6.0 ANALYSIS POPULATION

6.1 Efficacy Population

Intent-to-Treat (ITT) Population: The ITT population consists of all subjects, who met the inclusion/exclusion criteria and were randomized to receive one of the two devices. Efficacy analysis based on ITT population dataset will be the primary analysis.

Per-Protocol (PP) Population: The PP population includes all subjects, who met the inclusion/exclusion criteria and were randomized to receive one of the two devices and who had no significant violations, such as not receiving the assigned device. Efficacy based on the PP population dataset will be the secondary analysis.

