To preserve the controlled nature of this experiment, each subject will work with three experimenters. After completion of screening and enrollment, the subject will be assigned to either the active or control group by the Clinical Monitor (CM). The CM will use the randomization list provided by the Biostatistics group and the UW Institute for Clinical and Translational Research (ICTR) for this study, and will issue the appropriate device (Control or Active). The CM is the only person in the study who will know which group to which each subject is assigned. The PI will then instruct each subject in the features and use of the PoNS and follow a standardized stimulus intensity level setting procedure with the subject. The second investigator, specifically the Study Coordinator, will conduct and oversee all testing. A third investigator (Physical Therapist) will perform the actual intervention. Subjects will be instructed that they must not tell the therapist what they feel on their tongue, or ask questions about the stimulation since the PT will not be able to answer these questions. If the subject has questions or feels the need to report anything about the device or stimulation, they are to address these only to the PI, in confidence. This will prevent treatment and testing bias by ensuring that the therapists and Study Coordinator are blinded to the subjects' treatment group identity.

To help preserve the controlled nature of this experiment, subjects will also be instructed that they must not discuss the stimulation, the group they think they are in, or discuss details of the intervention with any other participants in the study or with family members. They may interact with other participants as long as their discussions are not related to the study. Subjects will be discouraged from congregating or socializing outside of the study in order to maintain blinding.

Lab study visits will take place at the Tactile Communication Neurorehabilitation Lab (TCNL) at [name]. Study duration is expected to be 3 years, from time of IRB approval to the completion of data analysis.

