- All candidates will have participated in a focused physical rehabilitation program for their TBI and feel that they have reached a plateau.
- All candidates will be able to understand and willing to give informed consent.

Exclusion criteria:

- All candidates that have oral health problems (e.g. gum disease, active cankers, cold sores, piercings, oral surgery within the previous 3 months).
- All candidates with non-removable metal orthodontic devices (e.g., braces) or oral cavity piercings that could interfere with PoNS[™] use.
- All candidates who have chronic infectious diseases (e.g. hepatitis, HIV, TB).
- All candidates with unmanaged hypertension.
- All candidates with unmanaged diabetes, or complications due to diabetes (e.g. retinopathy, neuropathy, renal disease).
- All candidates with neurological disorders other than those attributed to their primary diagnosis (e.g. MS, PD, ALS, AD or other dementia, uncontrolled pain).
- All candidates with a history of oral cancer.
- All candidates who have been treated for any type of cancer other than basal cell carcinoma within the past year.
- All candidates who have had a penetrating injury, craniotomy (with the exception of a burr hole (trephination) for resolution of acute subdural hematoma), or refractory subdural hematoma.
- Exceptions for other abnormalities identified in neuroradiologic scan reports that are asymptomatic and not expected to change may be made on a case by case basis by the Medical Advisor.
- All candidates with chronic use of psychoactive or psychostimulant medications that, in the opinion of the investigators, would compromise the subject's ability to comprehend and perform the study activities.

- All candidates who have a pacemaker, or are identified as at-risk for cardiovascular events.
- All candidates who are pregnant or lactating.
- All candidates with a lower extremity biomechanical prosthetic.
- All candidates with a history of seizures (except those in the acute or post-acute phases, and are controlled).
- All candidates who experienced a loss of consciousness greater than 24 hours as a result of their TBI.
- All candidates with a “severe” score in any of the Attention, Memory, or Executive Functions categories on the Cognitive Linguistic Quick Test (CLQT).
- All candidates who, in the opinion of the investigators, are unable to feel the stimulation and successfully complete the device level setting procedure.

Recruitment Process.

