Consent Process.

Candidates who have passed the phone screening will schedule a meeting with the Study Coordinator at the TCNL. The Study Coordinator will provide informed consent for the main TBI Study, answer questions and obtain informed written consent. Candidates may ask questions before signing the informed consent form. After completion of the TBI Study consent, the Study Coordinator will also provide informed consent for the [MRI Sub-study](#) and explain that participation in the sub-study is optional. All candidates will be informed that declining

participation in the MRI Sub-study will not affect their participation in the TBI Study. The PIs for both studies will be available to answer candidates' questions. All candidates are free to decline participation in either study without question if they so choose. Subjects will be given a copy of the signed consent form(s).

Subject Screening Procedure.

Once written informed consent has been obtained, the candidate will complete the Demographic Survey, the Subject Health Questionnaire, the CLQT, the SOT, and walk on the treadmill for 20 minutes. The results will be used to determine if the subject meets the study remaining entrance criteria. For those candidates that qualify for study, the SOT performed at screening will be recorded as the subject's baseline score.

Candidates who meet all screening criteria will be enrolled in the study and assigned a unique study identifier. Candidates that fail any portion of the screening will be excused from participation. All candidates who choose to enroll in the TBI Study will also be offered the opportunity to enroll in the MRI Sub-study.

Confidentiality of Screening Materials.

For persons who do not meet the entrance criteria, all personally identifiable records used for screening will be destroyed.

Compensation for Participation.

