Subjects will be paid for participation at the end of each phase of the study [\$800 after Stage 1 (2 weeks In-Lab), \$600 after Stage 2 (12 weeks in HTP), and \$600 after Stage 3 (12 weeks in withdrawal and 26 weeks total) for a total of up to \$2,000]. Subjects will be reimbursed for vehicle transportation costs from their residence to the lab for all visits (except screening), and for housing during Stage 1 if they live more than 30 miles from the UW-Madison campus. Reimbursement will be based on rates published by the University of WI for research subjects during the period of participation in the study. If a subject resides greater than 4 hours away from the lab, we will reimburse for mileage, if driving, or, if he/she chooses to travel by air, \$250 + 25% of the cost of round trip airfare for all visits (except screening). Reimbursement for airfare will be based up the requirements of the UW Air Travel Policy.

PoNS™ Device

Technical Description

The portable neuromodulation stimulator (PoNS™) device is held lightly in place by the lips and teeth around the neck of the tab that goes into the mouth and rests on the anterior, superior part of the tongue. The paddle-shaped tab of the system has a hexagonally patterned array of 143 gold-plated circular electrodes (1.50 mm diam., on 2.34 mm centers) created by a photolithographic process used to make printed circuit boards (Figure 6, lower right). The system has operational limits of 19 V (max) on the tongue (a nominal 5–7 k-ohm load). The biphasic waveform is specifically designed to ensure zero net dc current to minimize the potential for tissue irritation.

The PoNS 2.5 device has 2 user-controlled power buttons: “On” and “Off”. The stimulus intensity level for both the Active and Control PoNS v2.5 devices will be set by the PI in cooperation with the subject at the first training meeting and cannot subsequently be altered by anyone other than the PI. It has stimulation level, time, and date logging capabilities to monitor protocol compliance when off site. This feature allows for assessment of stimulus dose response. The system delivers

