Device Deployment

For each CN-NINM training session, participants will place the tab of the PoNS™ a maximum of 45 mm into their mouth so that it contacts the anterior, superior surface of the tongue. At the outset of CN-NINM training, subjects with the Active device will be instructed to adjust the stimulus intensity, to reach their minimum sensation threshold, S_t , and then the maximum level, S_m , without discomfort. The experimental stimulation intensity, $S_{e(A)}$, is calculated and pre-set to a value of 75% of the stimulus dynamic range, $S_m - S_t$, so that $S_{e(A)} = S_t + 0.75(S_m - S_t)$. Sensory adaptation occurs after 1-3 minutes of stimulation, requiring a small increase in the absolute intensity level. To accommodate for this adaptation and to avoid startle due to sudden onset of stimulation at S_e , the intensity will ramp up from S_t to S_e over a period of 30 seconds.

The Control device appears physically identical, but uses a modified stimulus waveform parameter set designed to elicit a mild tactile sensation while minimizing the net energy delivered, thereby minimizing any neuromodulatory effect. This is accomplished by using a pulse frequency that is slowed to approx. $1/2400^{\text{th}}$ that of the Active device. The Control group will be identically instructed to determine S_t and S_m , with the Control experimental stimulus, $S_{e(C)}$ preset [$S_{e(C)} = S_t + 0.75(S_m - S_t)$], to encourage compliance with the protocol by assuring that the subject can feel the stimulation.

Study Procedures & Research Interventions.

General Testing Plan: Upon enrollment in this research study the following testing will be conducted at baseline. These tests will take approximately 3 hours. The primary and secondary measures will be used to assess the effect of the intervention on the symptoms of balance and gait deficit. The observational measures will provide essential data for potential future studies investigating CN-NINM intervention specifically targeted to a particular function deficit. These same metrics will be applied during the course of the study according to the schedule in Table 6.

- outcome - NeuroCom CDP Sensory Organization Test (SOT) - Measures standing dynamic balance. Primary
- 6-Minute Walk Test - over ground (6MWT) - Measures walking speed.
- Dynamic Gait Index (DGI) – Assesses walking, walking with head turns, over and around obstacles, and stairs.

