** Video Nystagmography: Six standardized VNG tests (3 static: Horizontal fixation, Vertical fixation, Spontaneous nystagmus; and 3 dynamic: Random saccades, Smooth pursuit, Optokinetic) will be used to test and score subject eye fixation stability and movement control. VisualEyes™ is the standard for video nystagmographic observation, recording, and playback of ocular movements. Because the visual system is a primary contributor to motor, social, cognitive, and emotive functions, and oculomotor deficits require a significant, if unconscious, amount of attention in persons with TBI. Consequently, oculomotor monitoring methods that can observe this demand on the injured brain can be used to quantify any effects of neurorehabilitation due to the CN-NINM intervention.

Data Safety and Monitoring Plan

All study records will be structured and maintained as required under 21 CFR 812.140, and the investigators will make reports as required under 21 CFR 812.150.

Unanticipated adverse device effects

1. The PI and the Medical Advisor will immediately conduct an evaluation of any unanticipated adverse device effect.

2. If the investigators determine that an unanticipated adverse device effect presents an unreasonable risk to subjects, they shall terminate all investigations or parts of investigations presenting that risk as soon as possible. Termination shall occur no later than 5 working days after the investigators make this determination and no later than 10 working days after the investigators first received notice of the effect.
3. If the investigation was terminated due to unanticipated adverse device effects, the investigation may not resume without IRB approval.

Missing Data

We do not plan to recruit additional subjects to replace dropouts because we have increased the sample size to account for potential dropouts. We will make efforts to obtain follow-up data on subjects who withdraw from treatment. Due to the pilot nature of the study, we do not plan to do imputation for missing data points. Instead we will do a complete case analysis as well as a sensitivity analysis to examine the effect of the missing outcome data.

Compliance

We will respect the principle of Intention to Treat and will not remove subjects for protocol non-compliance. We have established the following *a priori* definition of compliance:

Subjects who miss more than 20% during any one-week period will be considered noncompliant with the training protocol.

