The primary outcome measure is the Composite SOT score. Observational measures are the Neurobehavioral Symptom Inventory, California Verbal Learning Test, Brief Symptom Inventory, Wechsler Adult Intelligence Scale – Symbol Search and Coding, Pittsburgh Sleep Quality Index, Headache Disability Index, Physiologic Stress Response, Quantitative Gait Assessment using EMG, 6 minute walk test, Dynamic Gait Index, and Computerized Video Nystagmography. The observational measures will provide essential data for potential future studies investigating CN-NINM effects on a particular functional deficit.

Data Analysis

An interim analysis will be performed when 22 subjects have completed the second phase (At-Home Training), and a full investigation at the completion of the study.

- **Interim Analysis:** In compliance with the request from the funding agency (US Army Medical Research and Materiel Command), a single independent interim analysis will be conducted under a Statistical Analysis Plan (SAP) developed for this study and reviewed by the Biostatistics Group at ICTR. The primary independent measure: Active vs. Control PoNS. The interim analysis will be performed after 22 subjects have completed the 6th data point (at 14 weeks - the completion of the At-Home phase of the study)

The primary analysis will be conducted under the intention-to-treat principal, and all data will be included. We will not conduct a missing data imputation analysis. Every attempt will be made to obtain follow-up data on subjects who withdraw from treatment.

The interim analysis will be performed using the primary efficacy endpoint for the data of first 22 subjects that have completed the Week 2 and Week 14 visits. The two treatment groups will be listed only as "Group 1" and "Group 2" to maintain the blinding of the treatments.

The number of subjects (most likely 11), and both the Mean and standard deviation (SD) for each group will be calculated by the study statistician. Student's *t*-test will be used to compare the two means. A *p*-value will be generated but no decision will be made at the interim analysis time, and the trial will continue to completion unless there are serious safety concerns.

The study statistician will present the interim analysis results (*n*, Mean, and SD) by treatment group in unblinded fashion including the *p*-value to the DSMC.

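### The SAP's primary ITT set leaves out randomised subjects judged ineligible, and one eligibility criterion appears to be judged after allocation, on a device that differs by arm

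*SAP*

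**What the plan says.** SAP 6.1 (Efficacy Population) states: "The ITT population consists of all subjects, who met the inclusion/exclusion criteria and were randomized to receive one of the two devices". It makes this set primary. The per-protocol set repeats the eligibility condition and adds the absence of significant violations, so no planned efficacy set contains everyone randomised.

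The protocol's Data Analysis section, under the interim analysis, says: "The primary analysis will be conducted under the intention-to-treat principal, and all data will be included". Its Compliance section invokes intention to treat but promises only that subjects will not be removed for non-compliance.

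On the criterion and its timing, the protocol says:

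- **Exclusion criteria:** candidates are excluded if, in the investigators' opinion, they are "unable to feel the stimulation and successfully complete the device level setting procedure".
- **Subject Screening Procedure:** "the candidate will complete the Demographic Survey, the Subject Health Questionnaire, the CLQT, the SOT, and walk on the treadmill for 20 minutes".
- **Study Design:** once screening and enrolment are complete, the Clinical Monitor assigns the arm and issues the device. Then: "The PI will then instruct each subject in the features and use of the PoNS and follow a standardized stimulus intensity level setting procedure".
- **PoNS Device, Technical Description:** the intensity level "will be set by the PI in cooperation with the subject at the first training meeting".
- **Device Deployment:** the Control device "uses a modified stimulus waveform parameter set designed to elicit a mild tactile sensation while minimizing the net energy delivered", with a pulse frequency about 1/2400th that of Active.

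**The concern.** An intention-to-treat set keeps the comparison that randomisation created. Adding an eligibility condition is fairly harmless if every criterion is settled before allocation, because arm cannot then influence who is removed. It is not harmless if a criterion is judged after allocation, by investigator opinion, from the response to a stimulus that differs between arms. Who stays in the primary set could then depend on the assigned device. If those removed would have had different SOT changes from those kept, the estimated treatment difference is biased. With 22 per arm and no replacement of dropouts, a few one-sided removals would carry weight.

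**Working it through.** **1. Order of events.** The screening steps in Recruitment Process and Subject Screening Procedure are the phone interview, document review, questionnaires, CLQT, SOT and treadmill walk. None uses the device, so the level-setting criterion cannot be judged from them. Study Design places level setting after assignment and device issue, Technical Description at the first training meeting, and Device Deployment at the outset of training. Table 4 has randomisation at the initial visit and training in Stage 1. These four places agree, and none mentions an earlier check on a common device.

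**2. The plan's own figure.** The inputs from SAP 3.1 are a difference of 26.3 − 13.2 = 13.1, SD 13.2, two-sided alpha 0.05 and a two-group t-test. Power comes from the noncentral t distribution with noncentrality (13.1/13.2)/√(1/n₁ + 1/n₂).

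- 17 per arm: noncentrality 2.89, 32 df, power 0.801. The stated 80% is reproduced.
- 22 per arm, all observed: noncentrality 3.29, 42 df, power 0.895.

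**3. Illustration of size.** The documents give no rate of level-setting failure, so the number dropped (k) and the gap (d) are assumptions. Suppose k of 22 subjects are dropped from one arm only, and their mean SOT change differs from that of the retained subjects by d SDs. The full-arm mean weights retained subjects by (22 − k)/22 and dropped subjects by k/22, so removal shifts that arm's mean by

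shift = (k/22) × d × 13.2.

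Type I error is the two-sided rejection probability of the t-test with 22 versus 22 − k subjects when the true difference is zero and the apparent difference equals the shift. Example, k = 4 and d = 1: shift = (4/22) × 13.2 = 2.40; noncentrality = 2.40/(13.2 × √(1/22 + 1/18)) = 0.572; 38 df; rejection probability 0.086.

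The power columns keep the true difference at 13.1 and reflect only the lost subjects.

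| k dropped | Shift, d = 0.5 | Shift, d = 1 | Type I, d = 0.5 | Type I, d = 1 | Power, 22 vs 22 − k | Power, 17 vs 17 − k |
|---|---|---|---|---|---|---|
| 0 | 0 | 0 | 0.050 | 0.050 | 0.895 | 0.801 |
| 1 | 0.30 | 0.60 | 0.051 | 0.052 | 0.888 | 0.788 |
| 2 | 0.60 | 1.20 | 0.052 | 0.060 | 0.880 | 0.774 |
| 3 | 0.90 | 1.80 | 0.055 | 0.071 | 0.871 | 0.757 |
| 4 | 1.20 | 2.40 | 0.059 | 0.086 | 0.861 | 0.739 |

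Relative to the planned difference, the shifts run from 0.3/13.1 = 2% to 2.4/13.1 = 18%.

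**The case against.** The best defence is that SAP 6.1 only describes a sequence: people are found eligible, then randomised. The exclusion speaks of candidates, the protocol enrols only those who meet all screening criteria, and assignment follows enrolment. SAP 5.2 plans the final analysis when all 44 subjects have completed Week 26, which suggests nobody expected eligibility removals. This reading is possible, and it is why the timing can only be said to appear post-allocation. It does not explain how this one criterion could be met from screening steps that involve no device.

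Second, failures may be few or balanced. Both arms get the same instructions and the same 75% formula, and the Control level is preset so that the subject can feel it. That stands: rate and direction are unknown, and the upper rows of the table's range have no empirical support. With one subject dropped the effect is negligible.

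Third, the sentence about including all data sits under the interim analysis and may have been written with withdrawals in mind. That softens the conflict but does not remove it. The interim and final analyses use the same primary endpoint, and no protocol statement on intention to treat carries an eligibility condition.

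Fourth, someone who fails level setting may have no later SOT, and the protocol's Missing Data section says: "Instead we will do a complete case analysis as well as a sensitivity analysis to examine the effect of the missing outcome data". The complete-case analysis would then drop that person however ITT is defined. This is correct, and it means that rewording SAP 6.1 is not enough without follow-up.

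**Conclusion.** The concern holds and should be fixed. The primary set is not intention to treat as defined. Followed as written, it allows randomised subjects to be removed on an investigator-judged criterion that appears to be applied after allocation and may depend on arm. If a pre-allocation check on a common device does exist, the arm-related route closes. SAP 6.1 would still permit dropping randomised subjects later found ineligible, contrary to the protocol's statement that all data are included.

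The size cannot be fixed from the documents. Under the assumed losses, bias runs from trivial (0.3 points, type I error 0.051) to material (2.4 points, 0.086). The loss of power is modest throughout; the main issue is the loss of the randomised comparison. Confidence is medium, because the timing of the criterion is inferred from the sequence and not stated.

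**What to change.** - **SAP 6.1:** define ITT as all randomised subjects, analysed in the arm assigned. Remove the eligibility condition from ITT and keep it in the per-protocol set only.
- **Follow-up:** keep subjects who fail level setting after allocation in SOT assessment at Weeks 2 and 14, so that the complete-case rule does not remove them instead. Report such failures by arm.
- **Protocol:** reconcile the level-setting exclusion with Study Design, Subject Screening Procedure and Technical Description, so that it is clear when, and on which device, the criterion is judged relative to randomisation.

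The cost is one clause in the SAP, one clarifying line in the protocol, and SOT visits for any such subject. Those visits fit the protocol's existing commitment to seek follow-up data on subjects who withdraw from treatment. No increase in sample size is needed. A few untreated subjects in ITT would dilute the effect slightly. If the eligibility clause was only meant to say that screening came first, removing it costs nothing.
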